1.3 Dose Rationale and Risk/Benefits

Local infiltration analgesia (LIA) involves injecting local anesthetic into the tissues around and within areas of the surgical wound, with the intent of providing satisfactory pain control, immediate mobilization of the surgical joint, and earlier discharge from the hospital.¹¹ Additional benefits for utilizing local infiltration analgesia techniques for the management of postoperative pain include its simplicity, decreased cost, reduced quadriceps weakness (in total knee arthroplasty patients), and reduction in risk of nerve injury following common peripheral nerve blocks.¹²

The use of interscalene brachial plexus nerve block remains the cornerstone for analgesia following shoulder surgery in comparison to suprascapular nerve block, intra-articular injection, and intravenous opioids.^{9,10} Local infiltration analgesia for shoulder surgery, despite showing to be less efficacious in terms of pain control, has not shown to be associated with adverse events.^{15,16} Theoretical advantages would include comparable pain scores to regional anesthesia techniques, while minimizing motor and/or sensory blockade as well as complications seen with interscalene brachial plexus blocks. Another advantage would be to avoid utilizing catheter based regional anesthesia techniques and its potential problems which include difficulty of catheter placement, catheter dislodgement, and leakage at insertion site. The theoretical advantages of local infiltration analgesia and the limited studies evaluating its use, particularly for total shoulder arthroplasty, are the basis for this study.

A complication associated with LIA would include local anesthetic systemic toxicity (LAST). Local anesthetic systemic toxicity is suspected if a patient has acute onset of central nervous system changes (tinnitus, metallic taste in mouth, perioral numbness) or cardiovascular changes (bradycardia, hypotension, EKG changes). This complication can occur with an intravascular injection, high systemic absorption depending on the vascularity of the site, and doses exceeding manufacturer's recommendation. LAST can also be seen with peripheral nerve blocks; therefore, the risk exists for all three intervention arms.

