3.3 Secondary Study Endpoints

1. Pain intensity (NRS) assessments prior to post-anesthesia care unit (PACU) discharge, every 4 hours beginning on arrival to patient room (to the closet time interval), and prior to hospital discharge or 12 pm on POD 1 (whichever comes first).
2. Opioid consumption in daily oral morphine equivalents (OME) – preoperative, intraoperative, PACU stay, and total beginning on arrival to patient room until patient discharge or up to POD 3 (whichever comes first).
3. Moderate to severe complications during regional anesthesia block placement (inadvertent intravascular injection⁺, inadvertent epidural or subarachnoid injection, local anesthetic systemic toxicity*, and pneumothorax) or during local infiltration analgesia injection (local anesthetic systemic toxicity).
 - a) ⁺*Inadvertent intravascular injection is suspected if a patient experiences sudden loss of consciousness, apnea, convulsions, hypotension, respiratory depression, nausea or dizziness, or stroke symptomology.*
 - b) ^{*}*Local anesthetic systemic toxicity is suspected if a patient has acute onset of central nervous system changes (tinnitus, metallic taste in mouth, perioral numbness) or cardiovascular changes (bradycardia, hypotension, EKG changes).*

4. Peripheral nerve block catheter-related complications including presence of site infection (tenderness to palpation, erythema, swelling, drainage of pus), hematoma, inadvertent catheter dislodgement, and local anesthetic systemic toxicity.
5. Duration of hospital stay (number of days), in addition to reason for hospital length of stay > 1 night (i.e., social work/disposition, inadequate pain control, nausea/vomiting, other)
6. Postoperative follow-up
 - a. Telephone encounter or office visit follow up 12 to 16 weeks postoperatively- NRS pain scores at rest and with movement of surgical extremity, postoperative neurologic changes (persistent numbness, paresthesia, or weakness of surgical extremity), and complications or adverse events will be noted.
7. Questionnaire Forms
 - a) SF-12
 - i. Collected preoperatively and at the 12-16 week postoperative visit or telephone call.
 - b) ASES
 - i. Collected preoperatively and 1-1.5 year postoperative visit or telephone call (data to be used in a follow-up study).
 - c) LANSS
 - i. Collected at 12-16 week follow-up visit to assess neuropathic pain in patients complaining of pain.

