3.4 Primary Safety Endpoints

These methods are already established procedures in the practice of perioperative pain control for a total shoulder arthroplasty. There is minimal risk of placing a peripheral nerve block. Those risks include infection, bleeding, and/or nerve damage. Patients will be monitored during the perioperative period for any adverse events (as defined below and in section 8). During regional anesthesia block placement, trained sedation nurses or anesthesia personnel (staff physicians, residents, or nurse anesthetists) will be monitoring patients. Patients will be monitored throughout the procedure utilizing the American Society of Anesthesiologists (ASA) standard monitors*, aspirating for blood or cerebral spinal fluid (CSF) prior to administration of local anesthetic solution in divided doses, frequent assessment of the patient's well-being via verbal communication, and having emergency medications and airway equipment readily available at all times. Performing this regional block is considered standard in our practice in order to provide optimal postoperative analgesia.

** blood pressure (non-invasive blood pressure cuff cycling every 3 to 5 minutes or continuous arterial blood pressure monitoring placed due to clinical judgment of covering anesthesiologist), 5 lead EKG, continuous pulse-oximetry, and continuous monitoring from operating room anesthesia personnel (if the procedure is performed in the operating room) or frequent assessments by nurses who are trained to care for patients receiving regional anesthesia blocks (if procedure is performed in block room)*

Patients undergoing local infiltration analgesia will have their block placed in the operating room by the surgeon under general anesthesia. Per ASA standards, trained anesthesia personnel will be directly monitoring the patient at all times during the surgical case, in addition to frequent

assessment of vital signs via standard monitors of care, which includes frequent blood pressure reading (blood pressure cuff or arterial line), rhythm analysis (5 lead EKG), heart rate (EKG), oxygen saturation (pulse-oximetry), temperature, and ventilation via end tidal carbon dioxide detection. Similar to regional block placement, blood pressure monitoring involves the following: non-invasive blood pressure cuff cycling every 3 to 5 minutes or continuous arterial blood pressure monitoring (placed due to clinical judgment of covering anesthesiologist).

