Patients admitted to the regular nursing floors will have a continuous pulse-oximeter if a continuous peripheral nerve block is present. In addition, vital signs (heart rate, oxygen saturation, and blood pressure) will be captured every 4 hours or more frequently if the clinical situation dictates in all postoperative orthopedic patients.

Daily follow-up will occur by the inpatient pain service and surgical team. Adverse events and/or complications will be monitored, which includes but not limited to, local anesthetic systemic toxicity, neurologic complications, hematoma, bleeding, infection, and wound problems. Nerve damage and assessment is part of the follow-up regarding this study and will be followed closely. In the event an infection was to occur, the PI would be notified, protocol would be followed, and investigators of the study would review the incident.

The principal investigator or a designated co-investigator of the study will be notified if a patient in the study requires an unanticipated ICU admission.

Please refer to section 8 for detailed explanation for management of adverse events or complications.

4 Subject Selection Enrollment and Withdrawal

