7.2 Statistical Methods

Descriptive Statistics

Baseline characteristics will be summarized using mean and standard deviation for continuous variables that have a normal Gaussian distribution, and median and interquartile range for continuous variables with a non-normal distribution. Frequencies and percentages will be used to summarize categorical baseline characteristics. Baseline characteristics will be compared across groups using analysis of variance, or the Kruskal-Wallis test for continuous variables and the chi square test for categorical variables.

The primary aim of this study is to assess whether continuous interscalene nerve block provides superior analgesic benefit via OBAS compared to single injection interscalene blockade and local infiltration analgesia on POD 1 for primary total shoulder arthroplasty. In order to test this hypothesis, the will be compared across groups using ANOVA (or the Kruskal-Wallis test). Supplemental pairwise comparisons will be performed using two-tailed tests with $\alpha=0.017$ (Bonferroni adjusted) used to denote statistical significance. Similar analyses will be performed for secondary endpoints of pain and total additional opioid medications (moeq) until hospital discharge.

NRS pain scores measured at arrival to PACU, PACU discharge, and every 4 hours until time of hospital discharge following surgery will be analyzed using repeated measures ANOVA with pairwise treatment comparisons performed using linear contrasts.

Postoperative complications will be compared across groups using the chi-square test and hospital length of stay (number of postoperative days) will be compared across treatment groups using the Kruskal-Wallis test with supplemental pairwise comparisons performed using the rank sum test. Similar analyses will be performed for additional endpoints collected at the 12-16 week follow-up visit including NRS pain scores and SF-12 scales.

Our primary analysis will be performed based on the intention to treat. All calculated p-values will be two sided. For the overall analyses comparing across all 3 treatment groups simultaneously p-values less than 0.05 will be considered statistically significant. For supplemental pairwise treatment group comparisons p-values less than 0.017 (Bonferroni adjusted) will be considered statistically significant. The statistical analysis will be performed using SAS version 9.4 (SAS Institute Inc., Cary, North Carolina, United States).

Handling of Missing Data

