8.5 Stopping Rules

Adverse events and serious adverse events, as defined in Section 8.1 of IND protocol, will be monitored by the study team for patient safety. Known serious adverse events associated with interscalene nerve blocks (SISB and CISB groups) include inadvertent intravascular injection⁺, local anesthetic systemic toxicity (LAST)*, inadvertent epidural or subarachnoid injection, and pneumothorax. Additionally, patients will be monitored throughout the procedure utilizing standard ASA monitors, aspirating for heme or cerebral spinal fluid (CSF) prior to administration of local anesthetic solution in divided doses, frequent assessment of the patient's well-being via verbal communication, and having emergency medications and airway equipment readily available at all times. Performing this regional block is considered standard in our practice and these methods are already established procedures in the practice of perioperative pain control for a total shoulder arthroplasty.^{4,5}

Serious adverse event associated with local infiltration analgesia (LIA group) is local anesthetic systemic toxicity (LAST).

⁺ *Inadvertent intravascular injection is suspected if a patient experiences sudden loss of consciousness, apnea, convulsions, hypotension, respiratory depression, or stroke symptomology.*

^{*} *Local anesthetic systemic toxicity is suspected if a patient has acute onset of central nervous system changes (tinnitus, metallic taste in mouth, perioral numbness) or cardiovascular changes (bradycardia, hypotension, EKG changes).*

LAST is a known serious adverse event with any local anesthetic administration. Preventive measures include high degree of suspicion, vital sign monitoring (blood pressure, EKG, oxygen saturation), using an appropriate dose of local anesthetic, injecting local anesthetic in divided dose, aspirating prior to injection of medication looking for heme, consider using epinephrine in solution as a vascular marker, being prepared to treat a LAST event immediately (checklist, external defibrillator, resuscitate medications, emergency airway equipment), and having lipid emulsion therapy readily available (standard of care).⁴⁶ We acknowledge that despite the rarity of these serious adverse events, the potential still exists.

Study stopping criteria includes:

CISB and SISB groups:

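### Section 3.3 counts the same complications by different rules in each arm, so a between-arm comparison built on items 3 and 4 is not like for like and risks favoring LIA

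*Combined protocol and SAP*

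**What the plan says.** Item 3 of section 3.3 opens with "Moderate to severe complications during regional anesthesia block placement (inadvertent intravascular injection" and goes on to epidural or subarachnoid injection, LAST and pneumothorax. For LIA it adds one event only: "or during local infiltration analgesia injection (local anesthetic systemic toxicity". Item 4 covers the catheter, hence CISB alone. It starts with site infection and ends with "hematoma, inadvertent catheter dislodgement, and local anesthetic systemic toxicity", and it carries no limit to the moment of placement. The secondary objectives in section 2 make the same split. The study schedule in section 6.3 marks catheter complications in three columns, read as Day 0, Day 1 and Days 2-5.

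On ascertainment, section 3.4 states: "Patients undergoing local infiltration analgesia will have their block placed in the operating room by the surgeon under general anesthesia". Section 5.7 says interscalene blocks are typically placed in awake patients. On the cause of LAST, section 1.3 states: "This complication can occur with an intravascular injection, high systemic absorption depending on the vascularity of the site".

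On analysis, section 7.2 states: "Postoperative complications will be compared across groups using the chi-square test". It does not list the complications meant. The LIA stopping rule in section 8.5 counts LAST without tying it to the injection.

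Section 8.5 also defines one item-3 event differently: "Inadvertent intravascular injection is suspected if a patient experiences sudden loss of consciousness, apnea, convulsions, hypotension, respiratory depression, or stroke symptomology". The definition in section 3.3 adds nausea or dizziness.

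**The concern.** A between-arm safety comparison is interpretable only if an event that can happen in every arm is counted by the same rule in every arm. LAST, infection and hematoma are such events, and items 3 and 4 treat them unequally. Sections 1.1 and 1.3 name fewer interscalene block complications as a theoretical advantage of LIA, so unequal counting would bear directly on a claim the trial may be used to support.

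The trial is unblinded (section 5.7), and section 6.4 takes outcomes other than OBAS from the database and chart review. The endpoint definition therefore guides what is abstracted. If section 7.2 leaves the compared outcome open, it can be settled after the results are known.

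**Working it through.** The plan gives no rate or power figure for complications, so there is none to reproduce. The only planning figure used is 43 patients per arm, 129 in all (section 7.1).

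**1. What items 3 and 4 count**

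| Event | LIA | SISB | CISB |
|---|---|---|---|
| LAST at injection or placement | yes | yes | yes |
| LAST later | no | no | yes, as catheter-related |
| Site infection | no | no | yes |
| Hematoma | no | no | yes |
| Intravascular injection; epidural or subarachnoid injection; pneumothorax | no | yes | yes |
| Catheter dislodgement | cannot occur | cannot occur | yes |

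Listed entries: LIA 1, SISB 4, CISB 4 + 4 = 8. LAST appears twice for CISB, so it has 7 distinct types. Rows 2 to 4 are the avoidable inequality. Dislodgement, and pneumothorax from a block needle, are real differences between techniques.

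**2. LAST in particular.** The definition needs either neurological symptoms that the patient reports or cardiovascular signs. In LIA's only item-3 window the patient is anesthetized, so only the cardiovascular half can be seen. Section 1.3 attributes LAST partly to systemic absorption, which is not confined to the moment of injection. LAST after emergence in an LIA patient falls outside item 3 but inside the section 8.5 stopping rule. LAST on the ward in a CISB patient falls inside item 4.

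**3. Possible readings of section 7.2**
- If all adverse events collected in every arm are compared, the inequality does not arise.
- If items 3 and 4 are compared event by event, LAST has unequal windows, and infection and hematoma are zero by definition in two arms.
- If items 3 and 4 are pooled, all the inequalities add together.

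The text does not choose among these.

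**4. Illustration, events common to all arms.** Assume LAST, infection and hematoma each have risk p in every arm, independently. CISB can register all three: P = 1 - (1 - p)^3. LIA and SISB can register LAST only, so at most p, and less if some LAST occurs later.

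| Assumed p | CISB | LIA or SISB, at most | Expected patients of 43: CISB vs at most |
|---|---|---|---|
| 0.5% | 1.5% | 0.5% | 0.64 vs 0.22 |
| 1% | 3.0% | 1.0% | 1.28 vs 0.43 |
| 2% | 5.9% | 2.0% | 2.53 vs 0.86 |
| 5% | 14.3% | 5.0% | 6.13 vs 2.15 |

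True harm is equal by construction, so the whole gap comes from the counting rule.

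**5. Illustration, if dislodgement were also pooled.** The documents give no dislodgement rate. At an assumed 5-15% of 43 catheters (2.15 to 6.45), about 2 to 6 patients are affected. For m events in CISB and none elsewhere, the exact three-arm p is 3 × C(43, m) / C(129, m), because every other split of m is more probable. The Pearson statistic is 2m × 129 / (129 - m) on 2 df, with p = exp(-statistic / 2).

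| m | Exact p | Pearson statistic | Pearson p |
|---|---|---|---|
| 2 | 3 × 903 / 8,256 = 0.33 | 4.06 | 0.13 |
| 3 | 3 × 12,341 / 349,504 = 0.11 | 6.14 | 0.046 |
| 6 | 3 × 6,096,454 / 5,688,177,600 = 0.0032 | 12.59 | 0.0018 |

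Expected counts are m/3, at most 2 per arm, so the chi-square approximation is poor here.

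**The case against.** The best defense is that the trial watches every arm. Section 3.4 states, without naming an arm: "Adverse events and/or complications will be monitored, which includes but not limited to, local anesthetic systemic toxicity, neurologic complications, hematoma, bleeding, infection, and wound problems". The schedule has adverse-event and neurologic rows through week 12-16, section 8.2 provides for specific questioning at daily encounters, and item 6a of section 3.3 records complications in all arms at 12-16 weeks. A reader might infer from item 3 that LIA patients can record nothing but LAST. That is true of items 3 and 4 but not of the trial.

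Item 4 can also be read as a description within CISB, and item 3 as intra-procedural, so neither need be what section 7.2 calls postoperative. No composite is named. By default the catheter comes out on POD 1, so the longer collection window does not imply a catheter in place throughout.

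On LAST, cardiovascular signs remain visible under continuous anesthesia monitoring, and changes in pulse or pressure during anesthesia might themselves be read as suspected LAST. Block patients may be sedated, so their symptom reporting is imperfect too. Item 3 is restricted to moderate or severe events, which weakens any argument that nausea or dizziness from sedation would inflate the block arms.

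Avoiding catheter problems is also part of the rationale for LIA, so dislodgement should stay visible.

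All of this narrows the point. It does not remove it: no text makes the all-arm data the compared outcome, the only in-hospital complication endpoints listed are items 3 and 4, and their rules for shared events are unequal as written.

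**Conclusion.** The point holds as a defect of definition. Items 3 and 4 apply different windows to LAST, and they count infection and hematoma in one arm only. Section 7.2 then plans a between-arm test without naming its events. A comparison built on these items is not like for like. The likely direction favors LIA, and also SISB relative to CISB.

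A reader might go further and conclude that the safety comparison is shown to be biased toward LIA. The documents do not support that: they give no event rates, do not state pooling, and leave part of the LAST definition observable under anesthesia. The threefold gap in step 4 rests on assumed equal and independent risks. The dislodgement example depends on an assumed rate and on pooling, and by the exact test it ranges from no signal (0.33) to a strong one (0.0032).

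This is a secondary safety endpoint; the primary OBAS analysis is unaffected. It should be corrected because the correction is cheap.

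**What to change.** - In sections 3.3 and 7.2, base the between-arm complication comparison on events possible in every arm: LAST, infection, hematoma or bleeding, and new neurologic deficit of the surgical limb. State which sites count for infection and hematoma, so that the needle or catheter site and the surgical wound are handled alike.
- Count these in all arms over one window, from the first local-anesthetic administration to a fixed in-hospital time point, plus the 12-16 week contact. Replace the injection-only wording for LIA, and the placement-only limit on LAST for the block arms, with that window. Section 8.1 sets a seven-week follow-up period for adverse events, so say explicitly that the later contact belongs to this outcome.
- Report dislodgement, epidural or subarachnoid injection and pneumothorax separately by arm, and do not pool them into that comparison.
- Reconcile the definitions of inadvertent intravascular injection in sections 3.3 and 8.5.

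The cost is wording, mirrored in section 2. Sections 3.4, 6.3 and 8.2 already provide for collecting these events in every arm, and no treatment changes. The trade-off is that technique-specific events do not enter the main comparison, although they remain fully reported.

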3.4 Primary Safety Endpoints

These methods are already established procedures in the practice of perioperative pain control for a total shoulder arthroplasty. There is minimal risk of placing a peripheral nerve block. Those risks include infection, bleeding, and/or nerve damage. Patients will be monitored during the perioperative period for any adverse events (as defined below and in section 8). During regional anesthesia block placement, trained sedation nurses or anesthesia personnel (staff physicians, residents, or nurse anesthetists) will be monitoring patients. Patients will be monitored throughout the procedure utilizing the American Society of Anesthesiologists (ASA) standard monitors*, aspirating for blood or cerebral spinal fluid (CSF) prior to administration of local anesthetic solution in divided doses, frequent assessment of the patient's well-being via verbal communication, and having emergency medications and airway equipment readily available at all times. Performing this regional block is considered standard in our practice in order to provide optimal postoperative analgesia.

** blood pressure (non-invasive blood pressure cuff cycling every 3 to 5 minutes or continuous arterial blood pressure monitoring placed due to clinical judgment of covering anesthesiologist), 5 lead EKG, continuous pulse-oximetry, and continuous monitoring from operating room anesthesia personnel (if the procedure is performed in the operating room) or frequent assessments by nurses who are trained to care for patients receiving regional anesthesia blocks (if procedure is performed in block room)*

Patients undergoing local infiltration analgesia will have their block placed in the operating room by the surgeon under general anesthesia. Per ASA standards, trained anesthesia personnel will be directly monitoring the patient at all times during the surgical case, in addition to frequent

assessment of vital signs via standard monitors of care, which includes frequent blood pressure reading (blood pressure cuff or arterial line), rhythm analysis (5 lead EKG), heart rate (EKG), oxygen saturation (pulse-oximetry), temperature, and ventilation via end tidal carbon dioxide detection. Similar to regional block placement, blood pressure monitoring involves the following: non-invasive blood pressure cuff cycling every 3 to 5 minutes or continuous arterial blood pressure monitoring (placed due to clinical judgment of covering anesthesiologist).

Patients admitted to the regular nursing floors will have a continuous pulse-oximeter if a continuous peripheral nerve block is present. In addition, vital signs (heart rate, oxygen saturation, and blood pressure) will be captured every 4 hours or more frequently if the clinical situation dictates in all postoperative orthopedic patients.

Daily follow-up will occur by the inpatient pain service and surgical team. Adverse events and/or complications will be monitored, which includes but not limited to, local anesthetic systemic toxicity, neurologic complications, hematoma, bleeding, infection, and wound problems. Nerve damage and assessment is part of the follow-up regarding this study and will be followed closely. In the event an infection was to occur, the PI would be notified, protocol would be followed, and investigators of the study would review the incident.

The principal investigator or a designated co-investigator of the study will be notified if a patient in the study requires an unanticipated ICU admission.

Please refer to section 8 for detailed explanation for management of adverse events or complications.

4 Subject Selection Enrollment and Withdrawal

